13.5 Analytical plan

All analyses will be conducted using an intention-to-treat approach. For our primary outcome, we will compare cluster level estimates of the incidence of malaria between intervention and control arms using a mixed effects Poisson regression model since randomization will occur at the district level (each district will include two clusters, randomized to the two study arms). We will also adjust our model for baseline estimates of malaria incidence (3 months prior to the intervention) and additional cluster-level covariates from the cross-sectional surveys including treatment seeking behaviour (to account for cases of malaria not captured at the MRCs) and the diagnostic accuracy of RDTs vs microscopy (to account for differences in the use of these diagnostic tests between clusters). The effect of the intervention will be expressed as an incidence rate ratio (incidence in the intervention arm/incidence in the control arm). Our primary analysis will evaluate malaria incidence over 24-months following the intervention. We will also perform secondary analyses of malaria incidence stratified by time following the intervention (year 1 vs year 2).

For our secondary outcomes, comparisons between intervention and control arms will be made using an individual-level approach to the analysis due to the large number of clusters per arm. Prevalence measures (parasitaemia, anaemia, LLIN ownership, LLIN coverage, LLIN access and LLIN use) will be compared using mixed effects logistic regression models with random effects at the level of the cluster and household. The effect of the intervention will be expressed as the prevalence ratio (prevalence in the intervention arm/prevalence in the control arm). For comparison of vector density, LLIN integrity, and bio-efficacy (funding permitting) between treatment arms, regression models will be used with generalized estimating equations to allow for within-cluster correlations. The effect of the intervention will be expressed as the density or rate ratio (density or rate in the intervention arm / density or rate in the control arm). Chemical analysis of withdrawn LLINs and their unused controls will be compared using the Wilcoxon rank sum test.

14 Ethical considerations

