7.3.2 Screening

When a household is identified, study personnel will briefly describe the purpose of the study to the head of the household (or their designate) in the appropriate language, and screen for eligibility (Appendix E).

The inclusion criteria are:

- 1 At least one adult aged 18 years or older present
- 2 Adult is a usual resident who slept in the sampled household on the night before the survey
- 3 Agreement of the adult resident to provide informed consent for the household survey

The exclusion criteria are:

- 1 Dwelling destroyed or not found

- 2 Household vacant
- 3 No adult resident home on more than 3 occasions

7.3.3 *Informed consent*

A detailed description of the informed consent procedures is provided in section 14.2. Briefly, study personnel will carry out the informed consent discussion with the head of the household (or their designate) in the appropriate language, and a translator will be used if necessary. The information sheets and consent forms will be available in English and the appropriate local languages. Following the consent discussion, the respondent will be asked by the study personnel to sign a written consent form to participate in a research study (consent form #1). If the respondent is unable to read or write, their fingerprint will substitute for a signature, and a signature from an impartial witness to the process will be obtained.

7.3.4 *Household survey questionnaire*

The household questionnaire (Appendix F) will be administered to the head of the household (or their designate), after obtaining their consent using a hand-held tablet computer. Information will be gathered on the characteristics of households and residents, proxy indicators of wealth including ownership of assets, and ownership and use of LLINs in the households, specifically focusing the nets distributed in the 2020-2021 LLIN campaign. The household survey questionnaire has been adapted from prior cross-sectional community surveys conducted in Uganda, including the national Malaria Indicator Surveys and the LLINeup trial [14, 38, 54, 55]. For the 12-month survey, we have added additional questions to assess knowledge, attitudes, and beliefs regarding COVID-19 and its effect on malaria care and control, as well as costs and treatment seeking behaviours for fever in the past two weeks.

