## 5.3 Community surveys

Cross-sectional community surveys will be conducted 12 and 24 months after nets are distributed. The surveys will include two components: (1) a household survey targeting heads of households, and (2) a clinical survey of children aged 2-10 years.

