#### 8.1.1 Analytical approach

All analyses will be conducted using an intention-to-treat approach according to the treatment allocations the clusters were randomized to. We will compare cluster level estimates of the incidence of malaria

between the intervention (PPF LLINs) and control arm (PBO LLINs) using a mixed effects Poisson regression model with a random effect at the district level (each district includes two clusters, randomized to one of the two study arms) and adjustment for log-transformed estimates of the baseline malaria incidence (3 months prior to the intervention) for each cluster. The effect of the intervention will be expressed as an incidence rate ratio (incidence in the intervention arm/incidence in the control arm). Our primary analysis will evaluate malaria incidence over 24 months following the intervention. We will also perform secondary analyses of malaria incidence stratified by time following the intervention (year 1 vs. year 2) and after adjusting for additional cluster-level covariates from the cross-sectional surveys including treatment seeking behaviour (to account for cases of malaria not captured at the MRCs) and the diagnostic accuracy of RDTs vs microscopy (to account for differences in the use of these diagnostic tests between clusters). These models will include random effects at the cluster level and we will assess the need for an additional random effect at the District level.

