### 9.2 Covariates

In the primary analysis of the primary outcome (malaria incidence) we will adjust for cluster level baseline estimates of malaria incidence (3 months prior to the intervention). In secondary analyses of the primary outcome we will adjust for additional cluster-level covariates from the cross-sectional surveys including treatment seeking behaviour (to account for cases of malaria not captured at the MRCs) and the diagnostic accuracy of RDTs vs microscopy (to account for differences in the use of these diagnostic tests between clusters).

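### Protocol 13.5 and SAP 8.1.1/9.2 specify different primary models for malaria incidence, and the protocol's extra covariates would in practice be measured after net delivery

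*Protocol*

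**What the plan says.** **Protocol 13.5.** One mixed effects Poisson model is described for the primary outcome. The authors will "adjust our model for baseline estimates of malaria incidence (3 months prior to the intervention) and additional cluster-level covariates from the cross-sectional surveys". In full, the survey part reads "additional cluster-level covariates from the cross-sectional surveys including treatment seeking behaviour (to account for cases of malaria not captured at the MRCs"), followed by the accuracy of RDTs against microscopy. The only secondary incidence analysis listed there is by period: "We will also perform secondary analyses of malaria incidence stratified by time following the intervention (year 1 vs year 2"). The survey-covariate model is not described as secondary.

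**SAP 8.1.1 and 9.2.** Section 9.2 states: "In the primary analysis of the primary outcome (malaria incidence) we will adjust for cluster level baseline estimates of malaria incidence". Section 8.1.1 gives the form: a district random effect and "adjustment for log-transformed estimates of the baseline malaria incidence (3 months prior to the intervention) for each cluster". The survey covariates have a different role: "In secondary analyses of the primary outcome we will adjust for additional cluster-level covariates from the cross-sectional surveys". SAP 8.1.1 closes by describing random effects for certain models (cluster level, with a district effect to be assessed), and it is not fully clear which models that sentence covers.

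**Timing.** SAP 5.3 states: "Cross-sectional community surveys will be conducted 12 and 24 months after nets are distributed". Protocol 7.3.4 says that, for the 12-month survey, questions were added on "costs and treatment seeking behaviours for fever in the past two weeks".

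**The concern.** The trial has one primary comparison, and the two documents give different covariate sets for it. Someone holding only the protocol would expect a different headline rate ratio from someone holding only the SAP. While both texts stand without a stated order of precedence, the choice between them could be made, or appear to have been made, after the results are known.

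The difference also matters for interpretation. Baseline incidence precedes the nets. Treatment seeking for fever, and test accuracy if it is estimated in febrile survey participants, are measured once the nets are in use. Net type could change how many fevers occur and how many of them are malaria. Adjusting for something the intervention has altered no longer estimates the total effect of allocation.

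**Working it through.** **1. Can the two texts be read as the same plan?** No. Protocol 13.5 lists baseline incidence and the survey covariates in one sentence about one model, and the year 1 versus year 2 split is its only secondary incidence analysis. The SAP assigns the same covariates explicitly to secondary analyses, in two places. The SAP also names a district random effect and a log transformation of baseline incidence. Protocol 13.5 names neither.

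**2. When can the survey covariates be measured in all 64 clusters?**
- Randomisation was complete when the protocol was developed (Protocol 4.3).
- Surveys in all 64 clusters are at 12 and 24 months (Protocol 4.1).
- A baseline survey depends on resources (Protocol 7.1). The timeline in section 15 marks one for October to December 2020, but the early survey that has funding is post-distribution, in 12 target areas (Protocol 7.4.6).
- Survey RDTs are done only in participants with measured or recently reported fever (Protocol 7.4.5 and 11.4). If these supply the accuracy covariate, it rests on febrile people.

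Post-delivery measurement is therefore an inference from the schedule. Protocol 13.5 does not state it.

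**3. Does the sample size settle which model was meant?** Protocol 13.4.1 gives control rate λ0 = 0.332 per person-year, IRR 0.74 (so λ1 = 0.332 × 0.74 = 0.24568), CV k = 0.42, 80% power and two-sided 0.05. Person-years per cluster, y, are assumed to be the minimum population times two years: 3000 (Protocol 13.2, 1500 persons) or 2400 (SAP 3.2, 1200 persons). The unmatched cluster formula for rates is

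c = (1.960 + 0.842)² × [(λ0 + λ1)/y + k²(λ0² + λ1²)] / (λ0 − λ1)²

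This gives 31.90 (y = 3000) or 31.95 (y = 2400), so 32 per arm. The stated figure is reproduced, with power of 80.1%. No covariate enters the formula, so it fits either model and does not decide between them.

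**4. Which way could the extra covariates move the estimate?** The documents give no inputs, so this is illustration only: 32 district pairs, true IRR 0.74, log-linear analysis of within-district differences, log-scale cluster SD 0.404.

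*(a) The covariate is partly a result of incidence.* Let it equal s × log incidence plus noise of SD 0.15. Baseline and residual components each have SD 0.6 × 0.404, and baseline is measured with error SD 0.2. The variance of the within-district difference after baseline adjustment is V = 0.2350 − 0.1175²/0.1975 = 0.165. The share of the log effect removed is f = s²V/(s²V + 2 × 0.15²), and the adjusted IRR is 0.74^(1 − f).
- s = 0.1: f = 0.035, IRR 0.75.
- s = 0.5: f = 0.478, IRR 0.85.

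The baseline-only model stays at 0.74. Simulation agrees (0.747 and 0.854).

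*(b) The covariate only changes case capture.* Let log capture differ by arm by δ, with between-cluster SD 0.15 and survey error SD 0.10. Baseline-only gives 0.74 × exp(δ). Adjustment removes the fraction 0.15²/(0.15² + 0.10²) = 0.692 of δ.
- δ = −0.2: baseline-only 0.61, adjusted 0.74 × exp(−0.0615) = 0.70.
- δ = +0.2: baseline-only about 0.90, adjusted 0.74 × exp(0.0615) = 0.79.
- δ = 0: both give 0.74.

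In (a) adjustment does harm, and in (b) it helps.

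**5. What if either model may be called primary?** A simulation under no effect (32 pairs, baseline correlation 0.6, 20 fevers per cluster, an uninformative RDT covariate, 8,000 runs per setting) rejected in 4.4% to 5.4% of runs for each model alone. Counting a rejection by either gave 5.9% to 7.8%. The verdicts differed in 2.1% to 6.3% of runs, depending on how strongly care-seeking drives capture.

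**The case against.** The SAP states its primary model twice and consistently, and it reads as the later text, since it reports net distribution in the past tense. On that view the working plan is already sound, and the inflation in step 5 could arise only if someone ignored SAP 9.2. Much of this stands, and it is why the repair is small. But neither document says that the SAP changes or supersedes protocol 13.5, so the removal of two prespecified covariates from the primary model goes unrecorded.

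The second objection is that the covariates have a legitimate purpose, namely correcting for cases that never reach the MRC and for differing test use. This also stands: illustration (b) shows adjustment reducing bias when capture differs by arm. It supports keeping those models as secondary analyses, which the SAP does.

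Three stronger readings are not supported:
- A reader might infer that treatment seeking is asked about solely for fevers in the last two weeks. Protocol 7.3.4 lists those questions as additions to the 12-month survey, and Protocol 10.2.2 describes wider questions on access to and use of care.
- A reader might infer that the bias can be sized by scaling the IRR by the ratio of care-seeking shares. The documents give no shares, and a regression coefficient on a noisy survey estimate does not make a full proportional correction. In a 32-pair simulation the IRR moved by 0.03 or less, in either direction.
- A reader might infer that net type changes RDT accuracy. The documents give no mechanism for that.

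**Conclusion.** The discrepancy is established from the text: the two documents define different primary models, and no precedence is stated. That the protocol's added covariates would be post-delivery follows from the survey schedule, because only the 12- and 24-month rounds are firm for all clusters.

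It does not follow that the protocol's model is biased by a known amount, or in a known direction. The illustrations run both ways and rest wholly on assumed inputs. The type I error of about 6% to 8% applies only if the choice of model is left open, and it too is simulated on assumed inputs. The stated 32 clusters per arm is unaffected.

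This should be corrected because it concerns the single primary comparison, with power of about 80% and so little margin. It does not call the design into question.

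**What to change.** State one primary model in both documents: the SAP's mixed effects Poisson model with log baseline incidence and a district random effect. Either align protocol 13.5 at the next amendment, or add a dated statement to the SAP that it supersedes 13.5 on this point. In both cases record the date relative to access to outcome data.

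Keep the models with treatment seeking and diagnostic accuracy as secondary analyses. Label them as using post-distribution covariates, and name the survey round that supplies them. Make clear which models the closing random-effects sentence of SAP 8.1.1 covers.

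The cost is a short text change and no new data. If it is made as a protocol amendment, Protocol 14.1 requires approval by all the listed review boards, of which there are five. The SAP statement would be the lighter route.

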- 1 *To evaluate the impact of PPF LLINs, as compared to PBO LLINs, on parasite prevalence, prevalence of anaemia, and (funding permitting) malaria vector density.* We will test the hypothesis that parasite prevalence, prevalence of anaemia and malaria vector density will be lower in intervention clusters (PPF LLINs), than in control clusters (PBO LLINs).
- 2 *To estimate the cost-effectiveness of delivering PPF LLINs, as compared to PBO LLINs.* We will estimate incremental cost-effectiveness ratios (USD per disability-adjusted life year averted and per malaria case averted).
- 3 *To assess net durability, bio-efficacy, survivorship and use of PPF LLINs vs PBO LLINs in Uganda.* We will conduct cross-sectional surveys to determine net survivorship, attrition and use, and if funding is available, will supplement these with laboratory assessments of net durability and bio-efficacy.
- 4 *To assess the impact of COVID-19 on malaria burden and care.* Through our cross-sectional surveys, we will estimate malaria parasite prevalence and seroprevalence of antibody responses to selected SARS-CoV-2 antigens, suggestive of prior infection with COVID-19, in individuals of all ages.

4 Study design & methods

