9.1 Overview

Funding permitting, a sub-set of LLINs distributed during the 2020-2021 universal LLIN campaign will be withdrawn (and replaced) from households enrolled into the 12- and 24-month cross-sectional community surveys to assess net durability. During each community survey, 248 households (4 per cluster, 124 per study arm), will be randomly selected from the 64 clusters to participate in the net durability study and will have one net withdrawn for durability assessment. A sample of 124 nets (one per household) of two different types, PPF LLINs (Royal Guard) and PBO LLINs (PermaNet 3.0) will be collected, packaged, labelled and stored. Each net collected will be replaced by a new net of the same type set aside by the NMCP/Ministry of Health.

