9.3 Chemical analysis of LLINs

If resources are available, HPLC will be conducted on samples of nets taken from the top surface of the LLINs withdrawn at the 24-month timepoint. The insecticides deltamethrin, alphacypermethrin, and pyriproxyfen, and the synergist PBO, will be extracted from the net samples using standard solvent extraction protocols, as in prior studies [54]. The chemicals extracted from the net will then be filtered to remove impurities before quantitative analysis performed via HPLC using controls of known insecticide concentration. This will allow the total concentration of insecticide and or synergist remaining on each net to be measured. Comparison to results of HPLC analysis on unused nets from the same distribution batch will allow the chemical degradation of the nets to be determined.

10 Economic evaluation

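### The optional 24-month net-chemistry outcome is planned only as an unclustered used-versus-new rank-sum test, with no estimate of content lost and no PPF-versus-PBO comparison of retention

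*Protocol*

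**What the plan says.** Objective 3 in Protocol section 3 is comparative: "To assess net durability, bio-efficacy, survivorship and use of PPF LLINs vs PBO LLINs in Uganda". It rests on the cross-sectional surveys, supplemented by laboratory work if money allows. Protocol 13.1 lists the concentration of insecticide or synergist remaining on each net as a secondary outcome, again subject to funding.

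Protocol 9.1 sets the net sample: "248 households (4 per cluster, 124 per study arm), will be randomly selected from the 64 clusters", with one net withdrawn per household. Protocol 9.3 covers the chemistry: "If resources are available, HPLC will be conducted on samples of nets taken from the top surface of the LLINs withdrawn at the 24-month timepoint". Four analytes are listed there: "The insecticides deltamethrin, alphacypermethrin, and pyriproxyfen, and the synergist PBO, will be extracted from the net samples". The stated purpose of the control nets is also there: "Comparison to results of HPLC analysis on unused nets from the same distribution batch will allow the chemical degradation of the nets to be determined".

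The analysis is one sentence in Protocol 13.5: "Chemical analysis of withdrawn LLINs and their unused controls will be compared using the Wilcoxon rank sum test". Just before it, the same section assigns vector density, LLIN integrity and bio-efficacy to between-arm regression with GEE, to allow for correlation within clusters, and expresses those effects as ratios.

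The SAP adds nothing on this point. Its objectives (2.1) and secondary outcomes (2.2.2) do not include net durability or net chemistry.

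**The concern.** The specified test asks whether used nets differ from new ones. After 24 months some loss is expected, so rejecting that null says little. The useful quantities are how much of each chemical remains and whether the fraction remaining differs between the two net types. The rank-sum test gives neither. Running it separately in each arm and setting the two p-values side by side would not estimate a PPF-versus-PBO difference.

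The test also treats the nets withdrawn from one cluster as independent. The neighbouring net outcomes are protected against this, and no reason is given for treating chemistry differently.

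Retention matters for interpretation. Protocol 13.5 plans incidence analyses for year 1 and year 2 separately, and faster loss of a partner chemical in one arm would help to explain an effect that fades or is absent. Protocol 10.1 also allows additional economic analyses with a shorter lifespan for one or both nets based on durability data, which calls for estimates specific to each net type. As written, the assays could be paid for and no planned between-arm estimate would result.

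**Working it through.** **Net sample.** 4 nets × 64 clusters = 256, or 128 per arm. The protocol states 248 and 124. Its figure corresponds to 248/4 = 62 clusters, 31 per arm. The gap is 8 nets (8/248 = 3.2%). This is a separate inconsistency in Protocol 9.1 that should be reconciled; it does not decide the present point. The stated 124 per arm is used below.

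**Assumed inputs.** The documents give no ICC for chemical content, no number of unused nets and no alpha for this test. Assumed here: ICC 0.05 to 0.30; 10, 30 or 124 unused nets per net type; two-sided 5%.

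**Formulas.** The design effect for 4 nets per cluster is DE = 1 + 3 × ICC. In the planned contrast only the used nets are clustered, so with m unused nets the ratio of true to assumed variance is

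R = (DE/124 + 1/m) / (1/124 + 1/m).

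The actual error of a nominal 5% test is 2 × (1 − Φ(1.96/√R)). In a naive arm-versus-arm test both groups are clustered and R = DE.

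**Example.** ICC 0.30, m = 124: DE = 1.90, R = (1.90 + 1)/2 = 1.45, 1.96/√1.45 = 1.63, error 10.4%.

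| ICC (assumed) | DE | Used vs unused, m = 10 | m = 30 | m = 124 | Naive arm vs arm (not planned) |
|---|---|---|---|---|---|
| 0.05 | 1.15 | 5.1% | 5.3% | 5.9% | 6.8% |
| 0.10 | 1.30 | 5.3% | 5.7% | 6.8% | 8.6% |
| 0.20 | 1.60 | 5.5% | 6.4% | 8.6% | 12.1% |
| 0.30 | 1.90 | 5.8% | 7.1% | 10.4% | 15.5% |

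**Simulation check.** The Wilcoxon test itself was simulated with 31 clusters of 4 nets per arm, 4,000 runs per scenario. For used versus unused at ICC 0.30, the error was 7.9% with 30 unused nets and 10.5% with 124. For arm versus arm it was 6.4%, 8.2%, 12.4% and 15.3% at the four ICCs. These agree with the formulas to within about one percentage point.

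**What a cluster-adjusted comparison would retain.** The effective number of nets per arm is 124/DE: 107.8, 95.4, 77.5 and 65.3 at the four ICCs. With 128 nets per arm it is 111.3, 98.5, 80.0 and 67.4. The standard error of a used-net mean grows by √DE, from √1.15 = 1.07 to √1.90 = 1.38. An arm comparison of retention therefore stays informative.

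**Scale.** Protocol section 2 describes the PPF net as alphacypermethrin plus PPF. By elimination from the analyte list, deltamethrin belongs to the PBO net. Raw concentrations of different compounds cannot sensibly be ranked across arms. The fraction of new-net content retained gives a common scale.

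**The case against.** The strongest defence is that the test matches its declared purpose. Protocol 9.3 says that the unused nets are there to measure degradation, and used versus unused is that contrast. Protocol 13.5 also says in general terms that secondary outcomes will be compared between arms. The first part stands as a reason to keep the unused nets, but a test without an estimate still does not measure degradation. The general sentence gives neither a method nor a scale for chemistry, and chemistry needs one because the compounds differ.

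Two stronger readings are tempting, and the documents do not support them.

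- A reader might infer that the PPF-versus-PBO durability objective cannot be answered. The synopsis defines durability by proportionate hole index, objective 3 rests first on the surveys, and 13.5 compares integrity and bio-efficacy between arms by GEE. Only the chemical component is affected.
- A reader might infer that the planned test runs at 6.8-15.5% error. Those figures belong to a naive arm-versus-arm test, which the protocol does not plan.

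A further fair objection is that if loss after 24 months is nearly certain, the null of no loss is false and type I error has little practical consequence. That is accepted: the clustering fault is secondary to the missing estimate.

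**Conclusion.** The point holds for the optional 24-month chemical outcome only. Protocol 13.5 specifies no estimate of content lost, no between-arm comparison of retention and no allowance for clustering, and the SAP does not supply them.

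The effect on error in the planned test is modest: about 5.1-5.9% at ICC 0.05 and 5.8-10.4% at ICC 0.30, across 10 to 124 unused nets. These ranges rest on assumed ICCs, assumed control numbers and an assumed two-sided 5% level. The absence of a planned PPF-versus-PBO estimate does not depend on any of these assumptions.

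Severity is minor: this is a secondary, resource-dependent laboratory outcome, and the primary outcome is untouched.

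**What to change.** In Protocol 13.5, replace the rank-sum test with a regression of log concentration on used/unused status, net type and their interaction, fitted once for the pyrethroid and once for the partner chemical (PPF or PBO). Use GEE or cluster-robust standard errors for the withdrawn nets. Keep the unused nets in the model as data. Dividing each used net by the mean of the unused nets would treat that mean as known and give intervals that are too narrow when controls are few.

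Report:

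- the geometric mean fraction retained for each chemical, with 95% CI;
- the between-arm ratio of retained fractions (the exponentiated interaction), with 95% CI.

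State the number of unused nets per net type. State also that partner-chemical retention compares different compounds, so equal fractions retained do not by themselves show equal retained effect; bio-efficacy addresses that.

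The cost is a change of wording and slightly more analysis work, with the same nets and assays. The intervals will be wider than an analysis that ignores clustering would give. The outcome stays subject to resources.
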